PIS	Participant Information Sheet
RCT	Randomised Control Trial
REC	Research Ethics Committee
SAE	Serious Adverse Event
SAR	Serious Adverse Reaction
SOP	Standard Operating Procedure
SmPC	Summary of Product Characteristics
SUSAR	Suspected Unexpected Serious Adverse Reaction
TMG	Trial Management Group
TSC	Trial Steering Committee

iii. TRIAL SUMMARY

Trial Title	A randomised, single blinded study investigating the role of 'Sambucol® Black Elderberry (Sambucus nigra) in the treatment, progression and reduction of symptoms in participants with Coronavirus 19	
Internal ref. no. (or short title)	BERRY	
Trial type	Food supplement trial	
Trial Design	Single Centre, placebo controlled, single blinded, two arm, randomised controlled trial.	
Trial Participants	Outpatients over the age of 18 with a positive COVID-19 swab result, after attending an East Kent Hospitals University NHS Foundation Trust site for swabbing, or a swabbing station booked through gov.uk website, or who contact the research team after seeing the approved posters or hearing about the trial through other external sources eg the media. And who have evidence of a positive test for COVID-19 within the last 5 days.	
Planned Sample Size	204	
Treatment duration	14 days	
Follow up duration	28 days	
Planned Trial Period	24 Months	
	Objectives	Outcome Measures
Primary Objective	Reduction in the severity of symptoms by 30% at day 10 in people who are symptomatic with the SARS-CoV-2 (COVID-19) virus treated with Sambucol vs. Placebo	Wellness VAS score
Secondary Objective	Reduction in admission to hospital by day 28. Reduction the severity of symptoms at day 3, 7, 14 and 28 days	Admissions to hospital Wellness VAS score
Treatments	Sambucol® Black Elderberry Original (Sambucus nigra) Liquid Placebo for Sambucol® Black Elderberry Original (Sambucus nigra) Liquid	
Formulation, Dose, Route of Administration	Liquid dose of 15ml orally, 4 times a day = Total 60ml per day	

iv. FUNDING AND SUPPORT IN KIND

FUNDER(S)	FINANCIAL AND NON FINANCIAL SUPPORT GIVEN
Pharmacare Europe Ltd. [name].	Non-Financial – free of charge supply of Sambucol and placebo
East Kent Hospitals University NHS Foundation Trust (EKHUFT)	Research support staff to carry out trial as non-funded.

v. ROLE OF TRIAL SPONSOR AND FUNDER

The sponsor is East Kent Hospitals University NHS Foundation Trust and will hold overall responsibility for the initiation and management of the trial.
 The required product and placebo will be provided by Pharmacare Europe Ltd.
 The sponsor is responsible for trial design, conduct, data analysis and interpretation, manuscript writing, and dissemination of results. The obligation in terms of the final decision regarding any of these aspects of the trial therefore lie with the sponsor.

vi. ROLES AND RESPONSIBILITIES OF TRIAL MANAGEMENT COMMITTEES

Trial Steering Committee (TSC)

The Trial Steering committee is a multidisciplinary group consisting of a group of members who jointly have responsibility for the design, conduct and evaluation of the clinical research project who will meet every 4 months and report to the sponsor.
 The role of the TSC is to provide overall supervision for a trial on behalf of the Trial Sponsor and to ensure that the trial is conducted to the rigorous standards set out in the Department of Health’s Research Governance Framework for Health and Social Care and the Guidelines for Good Clinical Practice.

Trial Management Group

The Trial Management Group will meet on a weekly basis due to the rapidly evolving nature of the COVID pandemic to ensure all practical details of the trial are progressing well and working well and everyone within the trial understands them.
 The trial will be conducted in compliance with the protocol, standard operating procedures, policies, local R&D management guidance, Good Clinical Practice including the Research Governance Framework.

vii. PROTOCOL CONTRIBUTORS

[figure not shown]
The protocol has been compiled with the input of clinicians, a pharmacist and an independent statistician who are experienced in NHS clinical trials. Overlooked by research delivery teams to ensure practical implementation of the protocol, and reviewed by the research and innovation department to ensure compliance as sponsor. Due to COVID-19 restrictions we have been unable to involve service users in the development of this protocol. However, results will be shared amongst the patient group.

viii. KEY WORDS:

Coronavirus symptoms, COVID-19, Sambucol®, Sambucus nigra, Elderberry, SARS-CoV-2

ix. TRIAL FLOW CHART

Berry Trial Flow Chart

1 BACKGROUND

The outbreak of the new coronavirus SARS-CoV-2 (COVID-19) in China has rapidly progressed to pandemic status of global importance. The current lack of a proven anti-viral that is effective has meant the current management of severe respiratory coronaviruses remains supportive. The success achieved in treating bacterial infections is not paralleled in antivirals. The relative paucity lies in a lack of drugs that stop replication within a living cell, and that the peak rate of growth may occur prior to symptoms.

A randomised controlled trial of lopinavir/ritonavir (an antiviral treatment commonly used to treat HIV) compared to standard of care in patients with severe COVID-19 demonstrated no clinical benefit and in 13.8% treatment had to be stopped early due to adverse events (1). Prophylactic use of hydroxychloroquine continues worldwide both within and outside of clinical trials but concern remains with prescribing an unproven drug with well-known adverse neurological and cardiac effects (2).

'RECOVERY' is a large UK randomised controlled trial established to test a range of potential treatments for COVID-19 in hospitalised patients, including lopinavir/ritonavir and hydroxychloroquine. Over 12,000 patients have been enrolled from 176 NHS hospitals. It showed no benefit of hydroxychloroquine nor lopinavir/ritonavir in this population, and by contrast, that low-dose dexamethasone reduces the risk of death by about one-third among patients receiving ventilation and by one-fifth in those requiring oxygen alone. However, no benefit was demonstrated amongst those not requiring respiratory support. (3)

Pharmacognosy is the study of medicines derived from natural sources. Plant extracts have been widely used to treat a number of medical conditions, with some of the best-known examples including, quinine isolated from *Cinchona pubescens* (cinchona tree) used to treat malaria, *Papaver somniferum* to make morphine and *Digitalis purpurea* for treating atrial fibrillation. A number of plant constituents have demonstrated anti-viral activity. Hippocrates, 'Father of Medicine' referred to Elderberry as 'natures medicine chest'.

In vitro *Sambucus FormosanaNakai* extract showed potent antiviral activity against human coronavirus NL63 in terms of decreased cytopathic effect and sub-G1 arrest in coronavirus infected cells. It produces a significant reduction in viral yield, plaque formation and virus attachment. The authors conclude that like *Sambucus nigra* L., *Sambucus FormosanaNakai* might possess antiviral features against the broad spectrum of human respiratory coronaviruses (4).

This supports the previously published data of *Sambucus* spp., and *Sambucus nigra* L. providing the antiviral properties against influenza A and B viruses and herpes simplex type 1 (5,6). Zakay-Rones et al 1995 demonstrated a significant improvement in symptoms in 93.3% of patients treated with standardised elderberry extract within 2 days compared to within 6 days in the control arm ($p < 0.001$). Complete cure occurred in 90% of those receiving the extract in 2 to 3 days (7). In subsequent randomised double-blind studies Zakay-Rones et al demonstrated no adverse events and significant improvement in clinical symptoms and higher antibody titres in those receiving *Sambuci fructus* (8).

Chen et al 2014 demonstrated with in vitro testing of coronavirus Infectious Bronchitis Virus (IBV) with *Sambucus.nigra* a reduction in virus titres by four orders of magnitude, compromised envelopes and membrane vesicles. This virion disruption likely renders it non-infectious (9). Of further interest was that complete inhibition occurred when pre-treatment of virus in combination with post-infection treatment.

SARS-CoV-2 (COVID-19) is a readily transmissible virus that has a wide-ranging incubation period of 2-14 days (US Centers for Disease Control and Prevention). The symptoms are often non-specific and include fever, cough, fatigue, diarrhoea and loss of sense of taste and smell. Clinical features range from mild to severe. Varying transmission patterns and mild symptoms are of concern as they facilitate rapid spread. Pre-existing potential drug therapies are under investigation, and only started once the patient has symptoms, but do have well established side effect profiles. Prophylaxis and prevention are currently dependent on social distancing and isolating with vaccines remaining in development, potentially not for mass use in the near future.

Sambucus extract has well documented anti-viral properties and no known drug interactions were identified in the literature. Hence, *Sambucus* maybe well suited for limited prophylaxis or treatment of mild/ moderate COVID-19. There is clear in Vitro evidence of activity against coronavirus and in human trials of influenza. The aim of this study is to see if Sambucol® Black Elderberry Original Liquid (*Sambucus nigra*) at a dose of 15ml, 4 times a day, reduces the duration or severity of symptoms of COVID-19. Symptomatic patients presenting to drive through testing (i.e. non-hospitalised) who test positive and who consent will be randomised to placebo or Sambucol® and blinded to treatment allocation. Study staff/investigators responsible for assessing outcomes and data analysis will also be blinded to treatment allocation. Data will be collected to determine resolution of symptoms and the two groups compared.

2 RATIONALE

There is a paucity of other pre-existing drug treatments changing the outcomes/symptoms in non-hospitalised patients with COVID-19. Evidence shows that *Sambucus.Nigra* has antiviral action against coronavirus in vitro and has been successful in treating influenza viruses in vivo. It is therefore likely that *Sambucus.nigra* may be effective in the treatment of COVID-19 in terms of reducing duration of symptoms and potentially progression to more severe disease.

Sambucol® Black Elderberry Original Liquid (*Sambucus nigra*) does not require a prescription and has no known side effects, meaning it would be a well-tolerated treatment in early disease in comparison with other postulated medications. The dose and route of administration for the trial is standard. A placebo arm will be used to ensure any reported affect is due to the Sambucol® only.

Currently there is no research looking into symptoms reduction on the wider outpatient community. This trial has the potential to target the disease progression in this outpatient population and thus reduce hospitalisation of COVID-19 patients. This will also have an impact on wider health economics enabling people to return to work sooner.

Aim: To determine whether ‘Sambucol® Black Elderberry Original Liquid (*Sambucus nigra*) is effective in reducing the severity of symptoms of COVID-19.

2.1 Assessment and management of risk

We anticipate this to be low risk trial given that Sambucol® Black Elderberry Original Liquid (*Sambucus nigra*) has never had reported adverse events/effects since commencing manufacture in 1991.

A thorough literature review has demonstrated there are no recorded side effects or drug interactions. Due to this it is classified as a food supplement and can be purchased freely without consultation or prescription, in food health shops and supermarkets, without limitation.

Vomiting and diarrhoea has been reported with the consumption of large volumes of raw and unripe fruit.

As with any product there is a potential allergy to the ingredients, hence those with known allergy will be excluded. As with all medicines, patients will be advised to seek urgent medical help if there are any signs of a severe allergy (i.e. difficulty breathing, swelling face/lips/ tongue).

With limited data on the effect in pregnancy and breast feeding this patient group has been excluded. Poorly controlled diabetics will be excluded due to the high sugar content.

The dose used is constant with no increments.

3 OBJECTIVES AND OUTCOME MEASURES/ENDPOINTS

3.1 Primary objective

Hypothesis - Sambucol reduces the severity of symptoms by at least 30% by day 10 in people who are symptomatic with the SARS-CoV-2 (COVID-19) virus, compared to placebo.

To determine whether Sambucol reduces the severity of symptoms by 30% by day 10 in people who are symptomatic with the SARS-CoV-2 (COVID-19) virus, as determined by VAS score.

3.2 Secondary objectives

To determine whether Sambucol reduces hospital admissions by day 28.

To determine if Sambucol reduces the severity of symptoms at day 3, 7, 14 and 28 days

3.3 Outcome measures

Reduction on symptom severity as per Wellness VAS Score

Reduction in hospital admission as per participant hospital admission rates

3.4 Primary endpoint

Primary endpoint will be the difference in number of patients by day 10 who have an improvement in reported SARS-CoV-2 (COVID-19) symptoms as per wellness VAS scale.

3.5 Secondary endpoints

Reduction in hospital admissions by day 28 as measured by rates of hospital admission

Reduction in the severity of symptoms at day 3, 7, 14 and 28 days as measured by wellness VAS Scale.

Reduction in the number of patients with mild/moderate disease progressing to severe disease (ITU /HDU admission)

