3.6 Exploratory endpoints - N/A

3.7 Table of objectives and outcome measures

Objectives	Outcome Measures	Timepoint(s) of evaluation of this outcome measure (if applicable)
Primary Objective Does Sambucol reduce the severity of symptoms by 30% at day 10 in people who are symptomatic with the SARS-CoV-2 (COVID-19) virus?	Patient Wellness VAS score	Day 10 score
Secondary Objectives Reduction in admission to hospital by day 28. Reduction in the severity of symptoms at day 3, 7, 14 and 28 days To determine of those admitted to hospital the number of patients with mild/moderate disease progressing to severe disease (ITU /HDU admission)	Admissions to hospital Wellness VAS score Number admitted to HDU/ITU	Within 28 days of enrolment Day 3,7, 14 and 28 Day 28 data

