Follow up telephone call within 5 days of a positive swab; Verbal Consent and Baseline data collection	Opportunity to raise and discuss any questions about the trial or PIS ^(a) . Eligibility criteria will be checked and electronic or verbal consent will be received. An eligible patient can decline to participate without having to give any reason. After consent, the research team will collect baseline demographics, VAS score, patient symptoms. ^(a)
Ineligible patients	If anyone does not meet the eligibility criteria the research team will explain why and ensure that they have time to ask any questions.
Randomisation and collection of trial treatment	Patients will be randomised to active or placebo liquid and a 14 day supply of study liquid dispensed to take home and start straight away. This can either be collected by a family member or friend and dropped to the patient's doorstep – or the research team will drop to the doorstep so that everyone has a chance to take part. If a participant lives further away the liquid will be delivered to their home address by courier.
Follow Up visits on day 3, 7, 10, 14 and 28	All follow up visits will occur either by phone, text or email depending on participant preference at day to collect the following data: 
 • Current symptoms

BERRY Protocol v 6.2 22.07.2021 IRAS 282732

	
 • How well are you feeling VAS score 0 -100 (0 will be recorded in the case of death) • What are your current symptoms? • Have you started any new medications? • Have you missed any doses of your study liquid? • Experienced any adverse events? • At day 14 – if a participant verbally consented initially, they will be asked to sign a paper consent form which was sent out with their trial liquid and return it in the research team for filing. At day 14 they will also be reminded that they need to stop taking their study liquid.
Notes	(a) This limits the exposure of the research team to the virus during later collection of written consent

BERRY Protocol v 6.2 22.07.2021 IRAS 282732

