7.8 Long term follow-up assessments

With the exception of any pregnancy outcomes, Data collection will end at day 28 following randomisation. Research team will follow up the outcomes of any notified pregnancies.

This will be to check to see if patients have been admitted to hospital in the 28 days following a positive SARS-CoV2 test.

If admitted:

- Date of hospitalisation
- Admission hospital and location (i.e. HDU/ITU) – reason and outcome. Date discharge / death

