9.5 Notification of deaths

The procedure for notification of death which does not constitute a SAR or SUSAR will be notification to sponsor by the chief investigator of only deaths that are assessed to be caused by the treatment will be reported to the sponsor. This report will be immediate.

9.6 Pregnancy Reporting Participants will be asked to report any pregnancy occurring within 28 days of trial enrolment. GPs will be asked for their assistance in relaying information regarding any pregnancies to the trial team. Any such pregnancies must be reported to the Chief Investigator and the Sponsor using the relevant Pregnancy Reporting Form. Pregnancy is not considered an AE unless a negative or consequential outcome is recorded for the mother or child/foetus. If the outcome meets the serious criteria, this would be considered an SAE.

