10.3.3 Secondary outcome analysis

Secondary outcomes with a baseline measurement at baseline will be analysed using equivalent methods to the primary outcome. Secondary endpoints measured on a categorical scale will be compared between groups using the Chi-square test.

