Appendix 2:

Classification of COVID19 severity

Severity	Symptoms/ signs
MILD	
Patients with uncomplicated upper respiratory tract viral infection, may have non-specific symptoms such as fever, fatigue, cough (with or without sputum production), anorexia, malaise, muscle pain, sore throat, dyspnoea, nasal congestion, or headache. Rarely, patients may also present with diarrhoea, nausea and vomiting.
 
The elderly and immunosuppressed may present with atypical symptoms.
 
Adult with pneumonia but no signs of severe pneumonia and no need for supplemental oxygen.

MODERATE	
Fever or suspected respiratory infection, plus one of: respiratory rate > 30 breaths/min; severe respiratory distress; or SpO2 ≤ 93% on room air.
 
Includes those managed on ward requiring oxygen support via nasal specs or mask

SEVERE/ CRITICAL	
Patient requiring HDU/ITU support.
 
Invasive ventilation.
 
Acute Respiratory Distress Syndrome.
 
Sepsis- life-threatening organ dysfunction caused by a dysregulated host response to suspected or proven infection.
 
Septic shock defined as persisting hypotension despite volume resuscitation, requiring vasopressors to maintain MAP ≥ 65 mmHg and serum lactate level > 2 mmol/L

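### The admission and HDU/ITU endpoints have no rule for death, so some deaths count as non-events or drop out

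*Combined protocol and SAP*

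**What the plan says.** Section 3.5 gives two binary secondary endpoints: "Reduction in hospital admissions by day 28 as measured by rates of hospital admission" and "Reduction in the number of patients with mild/moderate disease progressing to severe disease (ITU /HDU admission". Section 3.7 words the second differently: "To determine of those admitted to hospital the number of patients with mild/moderate disease progressing to severe disease (ITU /HDU admission". Its outcome measure there is the number admitted to HDU or ITU.

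On analysis, section 10.3.3 states: "Secondary endpoints measured on a categorical scale will be compared between groups using the Chi-square test". Section 10.7 puts all analyses on an intention-to-treat basis. Section 10.8 omits patients with missing data and does not impute.

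Death appears in four other places:

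- Section 7, follow-up visits, for the 0 to 100 VAS on how well the participant feels: "0 will be recorded in the case of death".
- Section 7.8, day-28 admission check: "Date discharge / death", in the list of items collected if the participant was admitted.
- Section 9.1, where an event resulting in death is a serious adverse event.
- Section 9.5, on notification: "only deaths that are assessed to be caused by the treatment will be reported to the sponsor".

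The severe/critical row of Appendix 2 begins "Patient requiring HDU/ITU support" and does not list death.

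**The concern.** Both endpoints are meant to capture worsening, and death is the worst form of it. Because they count only admissions, a death that bypasses the relevant admission leaves no mark on them. The plan foresaw death and gave it a value on the VAS, so the same participant can sit at the bottom of one secondary outcome and be a non-event on another. If such deaths were unevenly split between arms, the arm with more of them would show fewer events than its participants' true course warrants. Few events are likely on either endpoint, so one or two participants can matter.

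**Working it through.** **Step 1. Trace each kind of death through the definitions.**

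| Course by day 28 | Admission | Progression, 3.5 wording | Progression, 3.7 wording | VAS after death |
|---|---|---|---|---|
| Dies, never admitted | non-event | non-event | outside the denominator | 0 |
| Admitted, dies on an ordinary ward | event | non-event | non-event | 0 |
| Admitted, dies in HDU/ITU | event | event | event | 0 |

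The admission endpoint is affected only by deaths without any admission. Ward deaths affect progression only. Sections 3.5 and 3.7 disagree on where a home death goes.

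**Step 2. Reproduce the plan's own figure.** Section 10.1 uses SD 20, difference 10, 5% significance and 90% power. Taking the test as two-sided:

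n per arm = 2 × (1.960 + 1.282)² × (20/10)² = 84.06, which rounds up to 85. The t-test version gives 85.03, so 86, as stated. With 15% dropout, 86/0.85 = 101.2, so 102 per arm and 204 in total, as stated. This calculation rests on the VAS alone; nothing is stated for the two binary endpoints, so no documented figure changes.

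**Step 3. Weight of one death.** The documents give no event rates; the rates in this step and the next two are assumptions.

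- Admission at 5%: 102 × 0.05 = 5.1 per arm. One unadmitted death equals 1/5 = 20% of that count.
- HDU/ITU at 1% to 2%: 102 × 0.01 = 1.0 to 102 × 0.02 = 2.0 per arm. One death outside HDU/ITU equals 50% to 100% of that count.

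**Step 4. Chance of at least one unadmitted death among 204**, as 1 − (1 − q)^204:

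| Assumed risk q | Expected deaths (204q) | Chance of at least one |
|---|---|---|
| 0.1% | 0.2 | 18% |
| 0.5% | 1.0 | 64% |
| 1% | 2.0 | 87% |
| 2% | 4.1 | 98% |

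**Step 5. Effect on the test.** Uncorrected chi-square, 102 per arm, is equivalent to z = (difference in proportions) / √(2p̄(1 − p̄)/102), where p̄ is the pooled proportion. All unadmitted deaths are placed in the arm with fewer admissions, which is the unfavourable case.

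| Admissions | As written | 1 death counted | 2 counted | 3 counted |
|---|---|---|---|---|
| 4 vs 12 | p = 0.037 | 0.076 | 0.139 | 0.228 |
| 3 vs 10 | p = 0.045 | 0.097 | 0.180 | not run |

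For 4 vs 12, the difference falls from 7.8 percentage points to 6.9, 5.9 and 4.9. These tables were chosen to start just below 0.05. With 5 admissions in each arm, counting one death gives 6 vs 5: p̄ = 11/204 = 0.054, z = 0.0098/0.0316 = 0.31, p about 0.76, so nothing is concluded differently.

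**Step 6. Would omission under section 10.8 help?** For 4 vs 12 with three deaths dropped from the first arm (4/99 vs 12/102), p = 0.043, against 0.037 as written and 0.228 with the deaths counted. Omission hides the deaths almost as completely.

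**The case against.** The plan is silent on death in these endpoints. A reader might infer that it deliberately treats death as a good result, and the documents do not support that. The outcome follows from the definitions and the intention-to-treat rule, and section 10.3 leaves room for a full SAP, agreed before any data analysis, to settle it. That stands as to intent. It does not remove the gap: a participant's admission status up to death is in principle knowable, so section 10.8 on missing data does not naturally apply, and Step 6 shows it would not help.

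A reader might also infer that more deaths outside HDU/ITU make an arm look better on both endpoints. They do not: a ward death is already an admission event.

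The objective is hospital admission, and the rationale in section 2 is to reduce hospitalisation. Admission alone measures that directly, and an all-cause composite brings in deaths unrelated to COVID-19. This is a fair trade-off. It is met by reporting admission separately, which keeps the direct comparison.

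Appendix 2 is wider than HDU/ITU admission: it includes ARDS and sepsis, so some ward deaths could be classed as severe under it. But section 7.6 cites Appendix 2 for baseline severity, while sections 3.5 and 3.7 tie progression to HDU/ITU admission.

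Finally, that 0 is the worst VAS value is itself inferred, from the question asked and the death rule. The anchors are not given, and sections 10.1 and 10.3.2 call the measure a symptoms score.

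**Conclusion.** The point holds as a gap in two endpoint definitions. Followed literally, they record a death without admission as a non-event for admission, and a ward death as a non-event for progression. Under section 3.7, a home death drops out of progression. The VAS rule shows that death was foreseen but not carried across.

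The likely impact is small. These are secondary endpoints in outpatients, and the primary analysis and sample size are untouched. A reader might infer from Step 5 that the trial's conclusions are at risk. The documents do not support that: every rate and count there is assumed, and the sensitive examples were placed near the 5% boundary with all deaths in one arm. They show what is possible, not what is expected.

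A reader might also assume that rewording is enough because deaths are already collected. Section 7.8 lists date of death only for admitted participants, and section 9.5 limits notification. The VAS rule and serious adverse event recording under section 9.3 may pick up a home death, but no day-28 vital-status check is specified for every participant. This is a cheap improvement, not a flaw that threatens the trial.

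**What to change.** 1. In sections 3.5 and 3.7 and in the SAP, define the endpoints as *hospital admission or death from any cause by day 28* and *HDU/ITU admission or death from any cause by day 28*, both in all randomised participants.
2. Reconcile the section 3.5 progression wording with the restriction to admitted participants in section 3.7, so that there is one denominator.
3. Report admission, HDU/ITU admission and death separately by arm.
4. In section 7.8, record vital status at day 28, with date of death where it applies, for every participant.

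The cost is a few lines of text and one extra data field. The downside is a broader endpoint that can include deaths unrelated to COVID-19; the separate components let a reader see how much of any difference comes from these.
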